## 14. EXPLORATORY EXPOSURE-EFFICACY RESPONSE ANALYSIS

If deemed appropriate an exposure response analysis for the proportion of subjects who experience a HES flare during the 32-week study treatment period will be conducted.

### 14.1. Population of Interest

The exploratory exposure-efficacy response analysis will be performed on the ITT population.

### 14.2. Endpoints

Two separate measures of exposure will be considered for this analysis:

- i) Dose/bodyweight
- ii)  $C_{av} = \text{Dose}/(\text{Tau} * \text{CL}/F)$ ,

where CL/F is the PK model-estimated apparent systemic clearance for each individual, and Tau the (fixed) inter-dosing interval (28 days).

The efficacy endpoint analysed will be the primary endpoint of the proportion of subjects who experience a HES flare during the 32-week study treatment period. Subjects who withdraw from the study prior to Week 32 (Visit 11) and therefore have missing data on HES flares will be included in this analysis as treatment failures, i.e. a subject will be classed as not experiencing a HES flare only if they have no flares reported and complete Week 32 (Visit 11).

### 14.3. Methodology

A logistic regression model (linear, and if necessary, non-linear) will be fitted with exposure (dose/bodyweight or  $C_{av}$ ) fitted on the  $\log_e$  scale as a continuous covariate. The analysis will also be adjusted for region, baseline blood eosinophil count and baseline OCS dose. The odds ratio for each level of mepolizumab exposure versus placebo will be presented. Fractional polynomial models may also be explored in order to find the best fitting model for any relationship.

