4.2. Treatment Arms and Duration

- The study is comprised of a screening period of up to approximately 4 weeks followed by a 32-week study treatment period and up to 8-week additional follow-up period (12 weeks after the last dose of study treatment).
- Approximately 80 subjects who are able to maintain a stable regimen of HES therapy for the 4 weeks prior to Visit 2 will be randomized in a 1:1 ratio to receive either 300 mg mepolizumab *or* placebo SC every 4 weeks while continuing their HES therapy. The sample size may be increased up to a maximum of 120 subjects in total (Section 9.2.3). The same regimen of HES therapy will be maintained throughout the 32-week study treatment period unless there is worsening of symptom(s) that requires an increase in therapy. A reduction in dose for safety reasons, with return to the original dosing regimen if possible, is permitted in consultation with the GSK Medical Monitor.

- The final dose of study treatment will be administered at Visit 10 (Week 28) with completion of the study treatment period achieved at the next 4-weekly visit. At Visit 11 (Week 32), subjects will complete the end-of-treatment assessment (4 weeks after the last dose).
- Subjects who withdraw from study treatment prematurely should continue in the study per protocol (including HES flare-related assessments) until 32 weeks from randomization.
- For subjects whose last dose of study treatment is on Visit 9 (Week 24) or Visit 10 (Week 28) *and* who do not continue with open-label mepolizumab after completing Visit 11 assessment (32 weeks from randomization), there will be up to 8-week additional follow-up period, concluding with the 12 weeks post-last dose follow-up visit (Visit 12).
- Subjects will be eligible to be considered to receive open-label mepolizumab 300 mg SC every 4 weeks after *either*:
 - i. Completion of the treatment period in the 200622 study
 - or*
 - ii. If the subject was withdrawn from study treatment prematurely during the 200622 study, but continued in the study per protocol (including HES flare-related assessments) until 32 weeks from randomization.

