	
started blinded OCS (both active and placebo). The subject who has taken active blinded OCS will be instructed to continue with a new course of blinded OCS until the next scheduled clinic visit if the blood eosinophil count is at or above the threshold unless the subject's HES therapy has been increased due to a symptom flare since the initiation of the current course of blinded OCS, and discontinue if the blood eosinophil count is below the threshold. For subjects taking placebo-blinded OCS, continuation/discontinuation of blinded OCS will be determined depending on the continuation/discontinuation of their matched subject on active-blinded OCS.
 
 
• An open-label study is also planned (study 205203) for subjects who complete study 200622.
 

Main subject entry criteria	
 
• Subjects <math>\geq 12</math> years with HES
 
• At least 2 HES flares within the past 12 months; at least one HES flare within the past 12 months must not be related to a decrease in HES therapy during the 4 weeks prior to the flare.
 
• Blood eosinophil count <math>\geq 1000</math> cells/<math>\mu\text{L}</math> during screening. Investigators were permitted to use local laboratory results to meet this inclusion criteria.
 

Dosing	
 
• 300 mg mepolizumab or placebo SC every 4 weeks (8 administrations) while continuing their HES therapy.
 
• The final dose of study treatment will be administered at Visit 10 (Week 28) with completion of the study treatment period achieved at the next 4-weekly visit.
 

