### 9.3.1. Base Model

In consideration of the sparse sampling (3 samples post-start of treatment over 32 weeks: Week 4, 16 and 32) and the wealth of mepolizumab PK knowledge, the most recent population PK model will be applied directly to the dataset without estimation (e.g.  $\text{maxevals}=0$  in NONMEM) and predictions generated, against which the model will be validated prospectively using appropriate goodness of fit tests. For example, the Anderson-Darling and Cramér–von Mises tests are accepted methods of comparing Empirical Distribution Functions for model and data (i.e., PK concentrations) to evaluate whether independent observations (i.e., observed PK concentrations from the study) are adequately described by a model (i.e., most recent population PK model).

The following will be obtained:

- A description of the key models tested during the model development will be provided and tabulated;
- Population mepolizumab plasma PK parameter estimates with 95% CI from the final model will be tabulated. Goodness of fit plots for the final model will be presented;
- Individual post-hoc PK parameter estimates (such as area under the plasma concentration-time curve over the dosing interval [AUC (0- $\tau$ )],  $C_{AV}$  [AUC (0- $\tau$ )/ $\tau$ ]) will be summarised descriptively and listed;
- Individual post-hoc predicted plasma concentrations will be summarised descriptively and listed;
- Accumulation ratio estimate will be assessed at Week 16 and 32.

The most recent model consists of a two-compartment pharmacokinetic model with first-order absorption and elimination. Bodyweight is incorporated into the model using allometry with fixed physiological allometric exponents of 0.75 and unity for clearance and volumes, respectively. Albumin and creatinine clearance are also included as covariates of mepolizumab clearance on physiological grounds, however their effects are small and not of clinical relevance. Details of the model can be found in report GlaxoSmithKline Document Number [2015N238436\\_00](#).

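### With one 300 mg dose, SAP 14.3 cannot separate exposure from body weight: if weight predicts flare, all of that effect (dose/bodyweight) or part of it (Cav) can appear as an exposure effect

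*SAP*

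**What the plan says.** SAP 2.2 gives the dosing as "300 mg mepolizumab or placebo SC every 4 weeks (8 administrations) while continuing their HES therapy", so there is one active dose level.

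SAP 14.2 names two exposure measures. The first is "Dose/bodyweight". The second is Cav = Dose/(Tau × CL/F), "where CL/F is the PK model-estimated apparent systemic clearance for each individual", with Tau fixed at 28 days. On clearance, SAP 9.3.1 says: "Bodyweight is incorporated into the model using allometry with fixed physiological allometric exponents of 0.75 and unity for clearance and volumes, respectively". It adds: "Albumin and creatinine clearance are also included as covariates of mepolizumab clearance on physiological grounds", but describes both effects as small and clinically unimportant.

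SAP 14.3 fits a logistic model of the primary flare endpoint with log exposure as a continuous covariate. It allows non-linear and fractional polynomial forms and presents the odds ratio at each exposure level against placebo. On covariates it says only: "The analysis will also be adjusted for region, baseline blood eosinophil count and baseline OCS dose". SAP 14.1 uses the ITT population, so placebo subjects are included. Their exposure is zero, its log is undefined, and the section does not say how they enter the model.

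**The concern.** Within the active arm, exposure is not randomised. With dose constant, subjects differ in dose/bodyweight only because they differ in weight. They differ in Cav only because they differ in clearance, which itself carries weight. If heavier subjects flare more or less often for any reason unrelated to drug level, a model without weight has nowhere else to put that effect and assigns it to exposure.

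The output is a set of odds ratios by exposure level. A gradient produced by weight would look like an exposure-response relationship in a trial that enrols from age 12, where weights may be widely spread. The same mechanism could also hide a real relationship.

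**Working it through.** **Inputs from the documents.** One dose, 300 mg (SAP 2.2). 40 subjects per arm with flare in 60% on placebo and 22% on mepolizumab (Protocol 9.2.1). Allometric exponent 0.75 on clearance (SAP 9.3.1). Neither document gives a figure for the exposure-response analysis. Protocol 9.2.1 states 90% power for the primary comparison; exact enumeration with Fisher's test gives 91.9%, so the sample size and rates are used as stated.

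**Assumptions not in the documents.** SD of log weight s = 0.25 (range 0.20–0.30). Between-subject SD of log CL/F beyond weight ω = 0.30 (range 0.20–0.40). Weight odds ratio of 1.25, 1.5 or 2.0 per SD, equal in both arms. No true exposure effect. Region, eosinophils and OCS dose are left out of the calculation.

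**Step 1: what each measure contains.**
- log(dose/bodyweight) = log 300 − log W. Its correlation with log W is exactly −1.
- log Cav = constant − 0.75 log W − individual variation. Its correlation with log W is −0.75s/√(0.5625s² + ω²) = −0.1875/√(0.0352 + 0.09) = −0.53, ranging from −0.35 to −0.75 over the assumed inputs.

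**Step 2: treatment indicator plus a free exposure slope.** The true odds ratio is (0.22/0.78)/(0.60/0.40) = 0.188 at every exposure. For dose/bodyweight the false odds ratio per SD of exposure is the reciprocal of the weight odds ratio. At 1.5 the odds ratio versus placebo at the 5th and 95th percentiles is about 0.188 × 1.5^(±1.645), that is 0.37 and 0.10. Large simulated samples give:

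| Weight OR per SD | Dose/bodyweight: false OR per SD | OR v placebo, 5th to 95th percentile | Cav: false OR per SD | OR v placebo, 5th to 95th percentile |
|---|---|---|---|---|
| 1.0 | 1.00 | 0.19 to 0.19 | 1.01 | 0.19 to 0.19 |
| 1.25 | 0.81 | 0.27 to 0.13 | 0.90 | 0.23 to 0.16 |
| 1.5 | 0.67 | 0.37 to 0.10 | 0.81 | 0.28 to 0.14 |
| 2.0 | 0.50 | 0.62 to 0.06 | 0.70 | 0.38 to 0.12 |

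For Cav at 1.5, the share of the weight effect carried over on the log scale is ln 0.81 / ln 0.67 = 0.53, matching the correlation. Over the other settings tried, the false Cav odds ratio per SD is 0.75 to 0.87.

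**Step 3: trial size.** With 40 per arm, a nominal 5% test of the slope rejects as follows:
- Dose/bodyweight: 14% of the time at weight odds ratio 1.5 and 36% at 2.0.
- Cav: 6% and 12%.
- Either measure: about 4% when weight is not prognostic.

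**Step 4: other ways of entering placebo.**
- Single slope on log(1 + exposure), s = 0.25, median weight 72 kg assumed: the slope is −1.01 at weight odds ratio 1.5 and −0.99 at 2.0, so weight hardly moves it. But the fitted odds ratio is (1 + exposure)^slope, so any treatment effect forces a gradient. With s = 0.22 and weight not prognostic at all, the odds ratio runs from 0.26 to 0.14.
- Quadratic in log(1 + exposure), which the non-linear wording permits, s = 0.22 and weight odds ratio 1.5: 0.35 to 0.09. The weight effect returns.

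**Step 5: add log weight as a main effect, both arms, with a treatment term.** The exposure odds ratio per SD returns to 0.99–1.02 for both measures, and the odds ratio versus placebo to about 0.19 throughout. Slope-test rejection is 4–5%. The design matrix has full rank (4 of 4). In the active arm alone, dose/bodyweight and weight are collinear (rank 2 of 3), so placebo subjects must stay in the model.

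**The case against.** The distortion in the table depends on a model that SAP 14.3 does not write down. The section names one continuous exposure covariate and no treatment term, and a single slope through placebo is set mainly by the randomised contrast. This stands in part: the unstated placebo coding is half of the problem. It does not rescue the plan, because the single slope produces a gradient by construction and the permitted non-linear forms bring the weight effect back.

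A reader might infer that the whole prognostic effect of weight passes into both measures. It does so only for dose/bodyweight. Cav also varies with other determinants of clearance, so roughly 35–75% carries over on the assumed inputs.

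A reader might also take the list of long-term steroid effects in Protocol 2.2, which includes weight gain, as evidence that heavier subjects flare more. That list does not link weight to flare, and the model already adjusts for baseline OCS dose and eosinophils. Without a prognostic effect of weight there is no confounding.

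The scale also matters. At s = 0.22 and weight odds ratio 1.5, the false odds ratio per doubling of exposure is exp(−ln 1.5/0.22 × ln 2) = 0.28. But a doubling is ln 2/0.22 = 3.15 SD, nearly the whole 5th-to-95th percentile span of 3.29 SD; per SD the figure is 0.67. SAP 14.3 plans odds ratios rather than a slope test, so the rejection rates only illustrate the size of the effect.

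Finally, once weight is added, the dose/bodyweight slope is a treatment-by-weight interaction. It shows effect modification by weight, which need not act through exposure. That is a limit of a one-dose trial that no covariate removes.

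**Conclusion.** The structural point holds. With one dose, log(dose/bodyweight) carries no information beyond weight, Cav carries weight in part, and SAP 14.3 omits weight from the covariates. Where the within-active slope is free, a prognostic effect of weight is reported as exposure: fully for dose/bodyweight and about half for Cav on the central assumptions. At an assumed weight odds ratio of 1.5 per SD, a constant 0.188 is displayed as 0.37 to 0.10 and as 0.28 to 0.14 respectively. These sizes rest on assumed spreads of weight and clearance and on an assumed prognostic effect that neither document supports or excludes.

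The consequence is limited. SAP 14 makes the analysis exploratory and conditional, Appendix 10 lists its displays as post-SAC, and it lies outside the hierarchy in SAP 5.5. A reader might infer that the efficacy conclusion or a dosing decision is at risk; the documents tie this analysis to neither. It is a cheap improvement to an exploratory analysis.

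**What to change.** In SAP 14.3, specify for both exposure measures a logistic model with a treatment term, a treatment-by-log-exposure term, the covariates already listed, and baseline log_e(body weight) as a main effect in both arms. Keep placebo subjects in the model and state this coding explicitly. Use the same baseline weight in the covariate and in dose/bodyweight.

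Do not require albumin or creatinine clearance. SAP 9.3.1 regards their effects as small, and about 40 × 0.60 + 40 × 0.22 = 33 flares are expected. With two region terms, eosinophils, OCS dose, treatment, exposure and weight the model has 7 slope parameters (33/7 = 4.7 flares each). Two more would make 9 (3.7 each).

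The cost is a short addition to the SAP and one covariate already recorded at Visit 2 (Protocol 7.1). The interval for the exposure slope widens: on the assumed inputs at weight odds ratio 1.5, the standard error per SD rises from about 0.42 to 0.56 for dose/bodyweight and from about 0.41 to 0.44 for Cav.

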6. STUDY TREATMENT

6.1. Investigational Product and Other Study Treatment

The term ‘study treatment’ is used throughout the protocol to describe any combination of products received by the subject as per the protocol design. Study treatment may therefore refer to the individual study treatments or the combination of those study treatments.

	Study Treatment
Product name:	SB240563 (mepolizumab)
Formulation description:	Mepolizumab 100 mg vial for injection contains target quantities of 10.3 mg sodium phosphate dibasic heptahydrate, 0.96 mg polysorbate 80 and 230.4 mg xucose per vial.
Dosage form:	Lyophilized powder for injection reconstituted with Sterile Water for Injection, just prior to use.
Unit dose strength(s)/Dosage level(s):	3 vials (100mg/vial) per administration
Route of Administration	3 SC injections per administration
Dosing instructions:	Subjects will be dosed with three 100 mg SC injections every 4 weeks. Injections should be administered into the abdomen, upper arm, or thigh.
Physical description	Mepolizumab will be provided as a lyophilized cake in sterile vials for individual use.

If a subject becomes infected with helminths while receiving study treatment and does not respond to anti-helminth treatment, temporary discontinuation of study treatment should be considered in consultation with GSK Medical Monitor.

Mepolizumab

Mepolizumab is a humanized IgG antibody (IgG1, kappa) with human heavy and light chain frameworks. Mepolizumab will be provided as a lyophilized cake in sterile vials for single use. The vial will be reconstituted with Sterile Water for Injection just prior to use. Further details of dose preparation and administration can be found in the IB [GlaxoSmithKline Document Number [CM2003/00010/10](#)] and the unblinded reference manual.

Mepolizumab will be provided by GSK as open-label product to the unblinded site staff. Unblinded site staff are required for this study. Unblinded site staff will be responsible for receipt, storage, reconstitution, and labelling, and accountability of IP.

The placebo in this study will be 0.9% sodium chloride solution and will be provided by the study site.

The contents of the label will be in accordance with all applicable regulatory requirements.

Blinded OCS

GSK will provide blinded OCS. Each bottle will have a unique identifier number, and contain either 5 mg OCS (prednisolone or prednisone capsules) or matching placebo capsules. Refer to Section 6.4 for dispensing.

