Safety	
 
All subjects who are randomised and who receive at least one dose of study treatment. Randomised subjects will be assumed to have received study treatment unless definitive evidence to the contrary exists.
 
This population will be based on the treatment the subject actually received.
 
Subjects will be analysed according to treatment received for more than 50% of their treatment administrations. If a subject received an equal number of both treatments then they will be assigned to the treatment to which they were randomised.
 
	
 
Study Population
 
Safety
 

Pharmacokinetic	
 
All subjects in the ITT population who received
 
	
 
PK
 

Population	Definition / Criteria	Analyses Evaluated
	at least one dose of study treatment and for whom at least one PK sample was obtained, analysed and was measurable.	
Pharmacodynamic	
 
• All subjects in the ITT population who received at least one dose of study treatment and who also had a baseline PD measurement and at least one post-treatment PD measurement.
 
	
 
• PD
 

Refer to [Appendix 10](#): List of Data Displays which details the population used for each display.

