**7.1.5. Exploratory Modelling of Primary Endpoint**

The role of baseline blood eosinophil counts on the effectiveness of mepolizumab with respect to the proportion of subjects who experience a HES flare during the 32-week study treatment period will be investigated. A logistic regression model will be fitted, including baseline blood eosinophils fitted on the  $\log_e$  scale as a continuous covariate as well as a treatment-by-baseline blood eosinophils interaction term, in order to predict the odds ratio for mepolizumab vs placebo for each level of the baseline blood eosinophil count. The analysis will also be adjusted for region and baseline OCS dose, as described in Section 5.4.1. Fractional polynomial models may also be explored in order to find the best fitting model for the relationship.

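### The exposure-response model in SAP 14.3 takes the log of an exposure that is zero on placebo, so it cannot give the odds ratios versus placebo it promises

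*SAP*

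**What the plan says.** Section numbers are those of the amended SAP (18-JUN-2019), whose amendment list shows Section 14 as new.

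- **Status (14).** The analysis is optional: "If deemed appropriate an exposure response analysis for the proportion of subjects" with a flare. Its displays (Tables 7.5–7.6, Figures 7.9–7.10) are labelled Post-SAC.
- **Population (14.1).** "The exploratory exposure-efficacy response analysis will be performed on the ITT population". Section 4 defines ITT as everyone randomised, so the placebo arm is included.
- **Exposure (14.2).** Either dose/bodyweight or Cav = Dose/(Tau × CL/F), where CL/F "is the PK model-estimated apparent systemic clearance for each individual".
- **Model (14.3).** "A logistic regression model (linear, and if necessary, non-linear) will be fitted with exposure" on the log_e scale as a continuous covariate. The only other terms named are region, baseline eosinophil count and baseline OCS dose.
- **Output (14.3).** "The odds ratio for each level of mepolizumab exposure versus placebo will be presented".
- **Placebo (Protocol 6.1).** "The placebo in this study will be 0.9% sodium chloride solution".

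**The concern.** Both exposure measures are proportional to mepolizumab dose. A placebo subject has dose 0 and no drug concentrations from which to estimate CL/F, so log exposure does not exist for half the planned sample. Those same subjects are the reference for the promised odds ratio.

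The programmer must therefore improvise, and the obvious choices are poor. Dropping the undefined rows discards the comparator. Substituting a small number for zero produces a fit, but its single slope then carries the whole mepolizumab-versus-placebo difference. That difference would be reported as a trend across exposure, although every mepolizumab subject was assigned the same 300 mg dose. A reader could wrongly conclude that lighter or slower-clearing patients benefit more.

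Cav raises a smaller question. The PK population is limited to subjects "for whom at least one PK sample was obtained, analysed and was measurable", whereas ITT is not. Section 14.2 does not say which CL/F a mepolizumab subject without such a sample receives.

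**Working it through.** **1. Is there a rule elsewhere?** SAP 9.2 treats BLQ concentrations as missing. Sections 10.1.5 and 13.2 replace zero eosinophil counts, and 10.2.5 replaces BLQ IL-5 values. None covers dose/bodyweight or Cav. Section 7.1.5, which wants the same kind of output across baseline eosinophils, does specify a treatment-by-eosinophil "interaction term, in order to predict the odds ratio for mepolizumab vs placebo". Section 14.3 names nothing equivalent.

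**2. The model as written.** The SAP gives no figure to reproduce, so the model was fitted to an assumed dataset: 40 per arm, 24 placebo and 9 mepolizumab flares, weights evenly spaced from 45 to 110 kg, and no covariates. With log_e(0) = −∞ the fit fails. Dropping placebo leaves 40 subjects and no reference group; the slope within mepolizumab is −0.04, essentially flat.

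**3. Setting placebo to a constant c, same dataset.** The crude odds ratio is (9/31)/(24/16) = 0.194.

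| Handling of placebo | Slope | OR at 110 kg | OR at 75 kg | OR at 45 kg |
|---|---|---|---|---|
| c = half the lowest exposure (1.364 mg/kg) | −1.423 | 0.373 | 0.216 | 0.104 |
| c = 0.1 mg/kg | −0.443 | 0.231 | 0.195 | 0.156 |
| c = 0.01 mg/kg | −0.274 | 0.216 | 0.194 | 0.169 |
| c = 0.001 mg/kg | −0.198 | 0.209 | 0.194 | 0.175 |
| Indicator + centred log exposure | −0.044 | 0.197 | 0.194 | 0.189 |

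**4. Closed form at the design rates.** Protocol 9.2.1 gives 60% and 22%; the dose is 300 mg. Assumptions: 75 kg (4 mg/kg) as the typical subject, with 6 and 3 mg/kg (50 and 100 kg) as examples, and a slope determined by the arm contrast alone.

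- Design OR = (0.22/0.78)/(0.60/0.40) = 0.188; ln = −1.671.
- Slope = −1.671/ln(4/c); OR at x = exp(slope × ln(x/c)).
- c = 0.01: slope = −1.671/5.991 = −0.279. OR at 6 = exp(−0.279 × ln 600) = 0.168; at 3 = exp(−0.279 × ln 300) = 0.204.
- c = 1: slope = −1.671/1.386 = −1.205. OR at 6 = exp(−1.205 × ln 6) = 0.115; at 3 = exp(−1.205 × ln 3) = 0.266.
- At 4 mg/kg the odds ratio is 0.188 either way.

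**5. Simulation with no exposure effect inside the mepolizumab arm.** 4000 runs, 40 per arm, 60% v 22%, weight lognormal (median 75 kg, log-SD 0.2, assumed), no covariates. Median odds ratios at 6, 4 and 3 mg/kg:

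- c = 1: 0.115, 0.188, 0.265
- c = 0.01: 0.160, 0.180, 0.195
- indicator plus centred log exposure: 0.182, 0.173, 0.181

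Only the last shows no trend between 6 and 3 mg/kg, which is the truth in this simulation.

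**6. Why an indicator solves it.** Give placebo any finite code k and let the model contain a treatment effect b and exposure slope g. The log odds ratio at exposure x is b + g(log x − k). Changing k only shifts b, so the fitted odds ratios do not depend on it and g is estimated within mepolizumab alone.

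**The case against.** The strongest reply is that this SAP often leaves treatment implicit. The Cox model in 7.2.4.1 lists only baseline OCS dose and region, yet promises a hazard ratio, and a result expressed versus placebo suggests placebo was meant as the reference group. Section 14.3 also permits non-linear forms, some of which are defined at zero. On this reading the text is under-specified, not broken. The point about drafting style is fair. But reading in a treatment term still leaves the placebo rows with log_e(0), and the optional non-linear and fractional polynomial forms come with no zero rule; log and negative powers need positive exposure too.

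Three further points bear on size, and they stand. No passage says a constant will be used, so the false gradient is conditional on that workaround. The figures above set placebo to c; adding 1 mg/kg to every subject's exposure gives a weaker gradient, 0.133 at 6 mg/kg and 0.237 at 3, in the same direction. And with 40 per arm the sampling spread is wide: under the simulation's assumptions the central 95% of estimates from the indicator model runs from about 0.016 to 1.10 at 6 mg/kg, so the distortion with c = 0.01 is small beside the noise.

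On CL/F, no document says that any mepolizumab subject lacks a usable sample, and the population model in 9.3.1 could supply a prediction. That part is a request for clarification.

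**Conclusion.** The concern holds. The model stated in 14.3 cannot be fitted to the ITT population and so cannot deliver the odds ratios it promises. This follows from the documents alone. The size of any distortion does not: it depends on the workaround chosen and on assumed body weights. In the closed-form example the odds ratio moves from 0.168 to 0.115 at 6 mg/kg and from 0.204 to 0.266 at 3 mg/kg when the placebo value changes from 0.01 to 1 mg/kg.

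Severity is minor. Nothing confirmatory rests on an optional exploratory analysis reported after SAC, and the primary and secondary results are unaffected. It is still worth correcting, because two analysts following the text could report different exposure gradients from the same data.

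**What to change.** In 14.3, specify:

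- a treatment indicator with placebo as reference, plus log exposure minus its mean among mepolizumab subjects, set to 0 for placebo, alongside the covariates already listed;
- the odds ratio versus placebo at exposure x as exp(b_treatment + b_exposure × (log x − mean log x));
- for fractional polynomials, powers applied to the uncentred, positive exposure of mepolizumab subjects, with the transformed terms then centred and set to 0 for placebo. Centred log exposures can be negative (20 of 40 in one simulated arm), so powers should not be applied to them.

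In 14.2, state how mepolizumab subjects without an individual CL/F enter the Cav analysis, for example with the value predicted by the population model from body weight, albumin and creatinine clearance (9.3.1), and report how many there are.

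The cost is a few sentences of SAP text. The four displays stay; the Cav displays gain one count.
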